#### **11.4 Serious Adverse Event Reporting Procedures**

SAEs will be collected and recorded throughout the study period, beginning with the signing of the informed consent form through 90 days after the last dose of study drug or end of the study (if thought to be related to study drug), or 30 days after the initiation of a new anticancer therapy, whichever is earlier. All SAEs must be reported to Syndax or its representative within 24 hours of discovery or notification of the event. Initial SAE information and all amendments or additions must be recorded on a Serious Adverse Event Report Form and provided to Syndax or its representative. The SAE reporting procedure is provided in the Study Manual.

For all deaths, available autopsy reports and relevant medical reports should be provided to Syndax or its representative. If a patient is permanently withdrawn from the study because of an SAE, this information must be included in the initial or follow-up Serious Adverse Event Report Form as well as the EOT eCRF.

The Investigator should notify the IRB or EC of SAEs occurring at the site and other AE reports received from Syndax, in accordance with local procedures and statutes.

#### **11.4.1      Pregnancy and Lactation Reporting Procedures**

Although pregnancy and lactation are not considered AEs, it is the responsibility of Investigators or their designees to report any pregnancy or lactation in a patient (spontaneously reported to them) that occurs during the study or within 120 days of completing the study or 30 days following cessation of treatment if the patient initiates new anticancer therapy, whichever is earlier. All patients who become pregnant must be followed to the completion/termination of the pregnancy. Pregnancy outcomes of spontaneous abortion, missed abortion, benign hydatidiform mole, blighted ovum, fetal death, intrauterine death, miscarriage, and stillbirth must be reported as SAEs (Important Medical Events). If the pregnancy continues to term, the outcome (health of infant) must also be reported.

Such events must be reported within 24 hours to the Sponsor either by electronic media or paper. Sponsor Contact information can be found in the Study Manual.

Please refer to the Study Manual for further details on the pregnancy reporting procedure and associated report form.

#### **11.4.2    Definition of an Overdose for This Protocol and Reporting of Overdose to the Sponsor**

##### **11.4.2.1    Entinostat Overdose**

No information on the treatment of overdose of entinostat is currently available. Entinostat overdoses are defined as a single dose greater than 15mg. This overdose will not be considered an SAE unless the outcome of the overdose meets seriousness criteria as defined in [Section 11.2.4](#). In the event of an entinostat overdose, the Sponsor should be immediately notified. The patient should be carefully monitored for potential adverse reactions and symptomatic treatment instituted as per institutional standards of care.

##### **11.4.2.2    Pembrolizumab Overdose**

For this study, a pembrolizumab overdose will be defined as  $\geq 5$  times the dose for pembrolizumab (e.g.,  $\geq 1000$  mg). A pembrolizumab overdose is considered an SAE as described in [Section 11.4.3](#). No specific information is available on the treatment of overdose of pembrolizumab. In the event of overdose, the patient should be observed closely for signs of toxicity. Appropriate supportive treatment should be provided if clinically indicated.

#### **11.4.3 Events of Clinical Interest with Pembrolizumab**

Selected adverse events are also known as Events of Clinical Interest (ECI) and must be reported within 24 hours to the Sponsor according to the SAE Reporting Procedures as outlined in [Section 11.4](#). Sponsor Contact information can be found in the Study Manual.

ECIs for this study include:

1. An overdose of pembrolizumab, as defined in [Section 11.4.2](#), that is not associated with clinical symptoms or abnormal laboratory results.
2. an elevated AST or ALT value that is  $\geq 3 \times \text{ULN}$  and an elevated total bilirubin value that is  $\geq 2 \times \text{ULN}$  and, at the same time, an alkaline phosphatase value that is  $< 2 \times \text{ULN}$ , as determined by way of protocol-specified laboratory testing or unscheduled laboratory testing.\*

**\*Note:** These criteria are based upon available regulatory guidance documents. The purpose of the criteria is to specify a threshold of abnormal hepatic tests that may require an additional evaluation for an underlying etiology. The study site guidance for assessment and follow up of these criteria, called the Drug Induced Liver Injury and Overdose Guidelines, can be found in the Study Manual.

#### **11.4.4 Follow-Up of Adverse Events**

The Investigator must continue to follow all SAEs and non-serious AEs considered to be reasonably or possibly related to study drug either until resolution or the Investigator assesses them as chronic or stable. This follow-up may extend after the end of the study.

#### **11.4.5 Safety Reporting to Health Authorities, Ethics Committees/Institutional Review Boards and Investigators**

The Sponsor will send appropriate safety notifications to Health Authorities in accordance with applicable laws and regulations.

The Investigator must comply with any applicable site-specific requirements related to the reporting of SAEs involving his/her patients to the EC/IRB that approved the trial.

In accordance with ICH GCP guidelines, the Sponsor or designee will inform the investigator of “findings that could adversely affect the safety of study patients, impact the conduct of the trial, or alter the EC’s/IRB’s approval/favorable opinion to continue the trial.”

When specifically required by regulations and guidelines, the Sponsor or designee will provide appropriate Safety reports directly to the concerned health authority and lead EC / IRB and will maintain records of these notifications. When direct reporting by the Sponsor or designee is not clearly defined by national or site-specific regulations, the Investigator will be responsible for promptly notifying the concerned EC / IRB of any safety reports provided by the Sponsor or designee and of filing copies of all related correspondence in the Investigator Site File.

For trials covered by the European Directive 2001/20/EC, the Sponsor's responsibilities regarding the reporting of SAEs / SUSARs / Safety Issues will be carried out in accordance with that Directive and with the related detailed guidance.

#### **11.4.6 Protocol Deviations Due to an Emergency or Adverse Event**

Departures from the protocol will be determined as allowable on a case-by-case basis and only in the event of an emergency. The Investigator or other physician in attendance in such an emergency must contact the Medical Monitor as soon as possible to discuss the circumstances of the emergency.

The Medical Monitor, in conjunction with the Investigators, will decide whether the patient should continue to participate in the study. All protocol deviations and reasons for such deviations must be noted on the eCRF.

#### **11.5 Safety Monitoring**

The safety and tolerability of the investigational treatments will be monitored throughout the course of the study by the Investigators and the Sponsor Study Physicians(s) including the Medical Monitor.

The safety and tolerability data that will be reviewed will include, but are not limited to: AEs, DLTs, laboratory test results, and patient discontinuations. Additionally, the development of SAEs will be assessed by the Sponsor Study Physician(s) on a continuous basis. (Note that all SAEs must be reported to the Sponsor or designee within 24 hours of discovery or notification of the event [Section 11.4].)

No formal safety stopping rules are specified in the protocol. However, if any significant safety issues arise, a decision to modify or terminate the study will be made by the Sponsor in collaboration with the Investigators.

## 12. STATISTICAL CONSIDERATIONS

### 12.1 Sample Size Estimation

#### 12.1.1 Escalation Phase

Three to 6 patients will be enrolled in each dose cohort based on a standard Phase 1 dose escalation scheme. Each patient will participate in only 1 dose cohort. The total number of patients to be enrolled in the Dose Escalation/Confirmation Phase is dependent upon the observed safety profile, which will determine the number of patients per dose cohort, as well as the number of dose escalations required to achieve the MTD or RP2D.

A starting sample size of at least 3 patients per dose cohort, expanding to 6 patients in the event of a marginal DLT rate (33%) was deemed to be a safe and conventional approach in the dose escalation of a novel oncologic agent. Assuming a true DLT rate of 5% or less, there would be a 3% chance that dose escalation would be halted in a given cohort (i.e., observing 2 or more patients with DLT). If a true DLT rate of 50% is assumed, then there would be an 83% chance that dose escalation would be halted in a given cohort.

A total of 9- additional patients will be enrolled in the Dose Confirmation Cohort to obtain additional AE, immune correlate, and anti-tumor activity data on entinostat at the MTD or RP2D in combination.

#### 12.1.2 Expansion Phase

In the Expansion Phase of the study, the safety and preliminary antitumor activity of entinostat when administered at the RP2D with pembrolizumab will be explored in up to 4 cohorts of adult solid tumors as previously defined. Up to 252 patients are planned to be enrolled among the 4 cohorts. Patients will be enrolled in each cohort according to a single-arm study design with ORR, as determined by irRECIST, as the primary endpoint. The Expansion Phase will be carried out in 2 stages so that enrollment for 1 or more of the cohorts evaluated can terminate early in the event the antitumor activity of the combination regimen is not sufficient. The decision to terminate or continue enrollment for each cohort will be made independently of the other. The number of patients evaluated in each stage and the minimum number of responders needed to continue to the next stage, as described for cohort 1, was determined based on the optimum version of Simon's 2-stage design ([Simon 1989](#)), with 80% power and 1-sided significance level of 10%. For cohort 4, the number of patients evaluated in each stage and the minimum number of responders needed to continue to the next stage was determined based on the optimum version of Simon's

2-stage design, with 90% power and 1-sided significance level of 5%. For cohorts 2 and 3, the number of responders needed to declare the study a success was based on single proportion binomial test with 90% power and 1-sided significance level of 5%. Note that the protocol may be amended to allow for enrollment of additional or different cohorts, for example, patients with PD-L1-positive NSCLC, based on emerging data during study conduct.

Syndax will conduct one administrative analysis when at least 60% (42 out of 70 patients in cohort 2, 31 out of 52 patients in cohort 3) of patient information have accrued in cohorts 2 and 3 for decision making for late phase development planning. This administrative look will not lead to stopping of the study. Nonetheless, 0.01 alpha is being allocated to spend for the first administrative look and leaving 0.04 alpha for the final analysis.

***Cohort 1 (NSCLC patients with squamous cell and adenocarcinoma histology who have not been previously treated with a PD-1 or PD-L1-blocking antibody)***

A maximum of 46 patients will be enrolled in Cohort 1. A true ORR of 35% is hypothesized for both tumor types. An ORR greater than 20% is considered a lower threshold for antitumor activity that would warrant continued development. Based on the design elements specified above, up to 13 patients may be enrolled for either tumor type during the first stage: if 2 or fewer patients achieve an objective response (CR or PR), confirmed or unconfirmed, then enrollment will terminate; otherwise, 33 additional patients will be enrolled during the second stage. Upon completion of the second stage, if 13 or more patients out of the 46 enrolled achieve CR or PR, then the true ORR for the combination therapy likely exceeds 20%, the lower threshold of acceptable antitumor activity. Alternatively, if 12 or fewer patients achieve an objective response at the end of the second stage, then the true ORR is likely 20% or lower and further evaluation of the combination therapy may not be pursued for that tumor type. If the true ORR is 20% or less for a tumor type, then the expected sample size is 29.4, with probability of terminating enrollment at the end of the first stage equal to 50%.

***Cohort 2 (Patients with NSCLC (any histology) who have previously been treated and progressed on a PD-1 or PD-L1-blocking antibody)***

A maximum of 70 patients will be enrolled in Cohort 2. A true ORR of 15% is hypothesized. A response rate greater than 5% is considered the lower threshold for antitumor activity that would warrant continued development in this setting. Based on the design elements specified above, the single proportion (or one sample) binomial test will be used. Ninety-six percent 1-sided confidence interval of the observed one

sample proportion will be calculated. The trial will be considered a success if the lower limit of 96% confidence interval is greater than 5%.

Syndax will conduct one administrative analysis when at least 60% (42 out of 70 patients) of patient information have accrued in cohorts 2 for decision making for late phase development planning. This administrative look will not lead to stopping of the study. Nonetheless, 0.01 alpha is being allocated to spend for the first administrative look and leaving 0.04 alpha for the final analysis.

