***Cohort 3 (Patients with melanoma who have previously been treated and progressed on a PD-1 or PD-L1-blocking antibody)***

A maximum of 52 patients will be enrolled in cohort 3. A true ORR of 25% is hypothesized. An ORR greater than 10% is considered the lower threshold for antitumor activity that would warrant continued development in this setting. Based on the design elements specified above, the single proportion (or one sample) binomial test will be used. Ninety-six percent 1-sided confidence interval of the observed one sample proportion will be calculated. The trial will be considered a success if the lower limit of 96% confidence interval is greater than 10%.

Syndax will conduct one administrative analysis when at least 60% (31 out of 52 patients) of patient information have accrued in cohorts 3 for decision making for late phase development planning. This administrative look will not lead to stopping of the study. Nonetheless, 0.01 alpha is being allocated to spend for the first administrative look and leaving 0.04 alpha for the final analysis.

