#### **12.4.7 Safety Analysis**

Safety will be assessed by clinical review of all relevant parameters including AEs, SAEs, laboratory values, vital signs, and ECG results. Unless specified otherwise, the safety analyses will be conducted for the safety population defined in [Section 12.2](#).

Summary tables and listings will be provided for all reported TEAEs, defined as AEs that start on or after the first administration of study drug. The reported AE term will be assigned a standardized preferred term using the current version of the Medical Dictionary for Regulatory Activities (MedDRA).

TEAEs will be summarized based on the number and percentage of patients experiencing the event by MedDRA (version 18.0) system organ class (SOC) and preferred term. The causal relationship between the occurrence of an AE and study drug will be judged by the Investigator based on the conventions described in [Section 11.3](#). In the event a patient experiences repeat episodes of the same AE, then the event with the highest severity grade and strongest causal relationship to study drug will be used for purposes of incidence tabulations.

Tabular summaries will be provided for:

- DLTs (Dose Escalation/Confirmation Phase only)
- all TEAEs
- TEAEs by relationship to study drug and maximum severity grade
- TEAEs with action of study drug delayed/interrupted or dose reduced
- TEAEs with action of study drug discontinued
- SAEs

For the escalation phase, the observed DLT rate in each dose cohort will be calculated by the crude proportion of patients who experienced DLT with a 2-sided 95% exact binomial CI.

All deaths that occur on study (defined as during treatment or within 90 days of treatment discontinuation) will be reported in a patient listing, which will include the primary cause of death and the number of days between the date of the last dose of study drug and death.

Hematology, serum chemistries, and vital signs will be summarized in a descriptive manner by calculating the mean, standard deviation, median, and range as follows:

- baseline value
- minimum post-baseline value
- maximum post-baseline value
- average post-baseline value

- last post-baseline value

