combination therapy may not be pursued for that tumor type. If the true ORR is 20% or less for a tumor type, then the expected sample size is 29.4, with probability of terminating enrollment at the end of the first stage equal to 50%.

Cohort 2 (Patients with NSCLC (any histology) who have previously been treated and progressed on a PD-1 or PD-L1-blocking antibody)

A maximum of 56 patients will be enrolled in Cohort 2. A true ORR of 15% is hypothesized. A response rate greater than 5% is considered the lower threshold for antitumor activity that would warrant continued development in this setting. Based on the design elements specified above, up to 20 patients may be enrolled during the first stage: if 1 or no patients achieve a CR or PR, confirmed or unconfirmed then enrollment will terminate; otherwise 36 additional patients will be enrolled during the second stage. Upon completion of the second stage, if 5 or more patients out of 56 enrolled achieve CR or PR, then true ORR for the combination regimen likely exceeds 5%, the lower threshold of acceptable antitumor activity. Alternatively, if 4 or fewer patients achieve an objective response at the end of the second stage, then the true ORR is likely 5% or lower and further evaluation of the combination therapy may not be pursued in this setting. If the true ORR is 5% or less, then the expected sample size is 29.5, with probability of terminating enrollment at the end of the first stage equal to 74%. However, with Amendment 5, the study design for this cohort is changed from Simon 2-stage design to single proportional binomial test after moving in to 2nd stage. Based on single proportional binomial test, maximum of 70 patients are enrolled in Cohort 2.

Ninety-six percent 1-sided confidence interval (or 92% 2-sided confidence interval) of the observed one sample proportion will be calculated. The trial will be considered a success if the lower limit of 96% confidence interval is greater than 5%.

Syndax will conduct one administrative analysis when at least 60% (42 out of 70 patients) of patient information has been accrued in cohort 2 for decision making for late phase development planning. This administrative look will not lead to stopping of the study. Nonetheless, 0.01 alpha is being allocated for the first administrative look, leaving 0.04 alpha for the final analysis.

Cohort 3 (Patients with melanoma who have previously been treated and progressed on a PD-1 or PD-L1-blocking antibody)

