A maximum of 34 patients will be enrolled in Cohort 3. A true ORR of 25% is hypothesized. A response rate greater than 10% is considered the lower threshold for antitumor activity that would warrant continued development in this setting. Based on the design elements specified above, up to 13 patients may be enrolled during the first stage: if 1 or no patients achieve a CR or PR, confirmed or unconfirmed then enrollment will terminate; otherwise 21 additional patients will be enrolled during the second stage. Upon completion of the second stage, if 6 or more patients out of 34 enrolled achieve CR or PR, then true ORR for the combination regimen likely exceeds 10%, the lower threshold of acceptable antitumor activity. Alternatively, if 5 or fewer patients achieve an objective response at the end of the second stage, then the true ORR is likely 5% or lower and further evaluation of the combination therapy may not be pursued in this setting. If the true ORR is 10% or less, then the expected sample size is 20.9, with probability of terminating enrollment at the end of the first stage equal to 62%. However, with Amendment 5, the study design for this cohort is changed from Simon 2-stage design to single proportional binomial test after moving in to 2nd stage. Based on single proportional binomial test, maximum of 52 patients are enrolled in Cohort 3. Ninety-six percent 1-sided confidence interval (or 92% 2-sided confidence interval) of the observed one sample proportion will be calculated. The trial will be considered a success if the lower limit of 96% confidence interval is greater than 10%. Syndax will conduct one administrative analysis when at least 60% (31 out of 52 patients) of patient information has been accrued in cohort 3 for decision making for late phase development planning. This administrative look will not lead to stopping of the study. Nonetheless, 0.01 alpha is being allocated for the first administrative look, leaving 0.04 alpha for the final analysis.

Cohort 4 (Patients with CRC who have not previously been treated on a PD-1 or PD-L1-blocking antibody)

A maximum of 84 patients will be enrolled in Cohort 4. A true ORR of 15% is hypothesized. An ORR greater than 5% is considered the lower threshold for antitumor

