3.8 Efficacy Analysis

Efficacy analyses will be performed using the FAS and, where appropriate, the Per-Protocol Set. ORR will be estimated for each cohort evaluated in the Expansion Phase using irRECIST as the primary endpoint. Crude proportion of patients with best overall response of CR or PR, along with a 2-sided 95% CI, will be calculated for each cohort. The width of the CI will be adjusted to account for the multistage design (Atkinson, 1985). Additionally, a 90% one-sided CI of the form $(\pi, 1]$ will be reported for cohort 1 and a 95% one-sided CI will be reported for cohort 4 since the sample size for the Expansion Phases for cohorts 1 and 4 were determined using a one-sided significance level of 10%, 5%, respectively.

Crude proportion of patients with best overall response of CR or PR, along with a 2-sided 92% CI will be calculated for cohorts 2 and 3. ORR based on RECIST 1.1 will be analyzed in a similar manner.

Clinical Benefit Rate

Clinical benefit rate, as determined by irRECIST, will be estimated based on the crude proportion of patients in each cohort whose best overall response during the course of study treatment is a irCR, irPR, or irSD lasting for at least 6 months. Stable disease based on irRECIST will be measured from the start date of study treatment until the criteria for irPD is first met. Approximate 2-sided 95% CIs will be calculated for each cohort. Clinical benefit rate, as determined by RECIST 1.1, will be estimated based on the crude proportion of patients in each cohort whose best response during the course of study treatment is a CR, PR, or SD lasting for at least 6 months. Stable disease based on RECIST 1.1 will be measured from the start date of study treatment until the criteria for PD is first met. Approximate 2-sided 95% CIs will be calculated for each cohort.

Progression-free Survival

The PFS, defined as the number of months from first dose date to PD or death due to any cause, whichever occurs first. Disease assessments will continue until PD, even

after the originally assigned study treatment is discontinued. For purposes of analysis, 1 month is considered 30.4375 days. The duration of PFS as determined by RECIST 1.1 (Eisenhauer 2009) and irRECIST (Seymour 2017) will be summarized descriptively using the Kaplan-Meier method (Kaplan 1958). The PFS at 6 months by irRECIST and RECIST 1.1 will be analyzed in a similar manner.

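### Cohorts 2 and 3: no responder cut-off at 70 or 52 patients gives both one-sided 5% and 90% power, and the 96% success limit has no named method or count

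*Protocol*

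**What the plan says.** Protocol 12.1.2 sets the design level for Cohorts 2 and 3: the responder number for "success was based on single proportion binomial test with 90% power and 1-sided significance level of 5" percent. It assigns 0.01 of that alpha to a non-stopping administrative look and leaves 0.04 for the final analysis. For each of the two cohorts it adds that "the single proportion (or one sample) binomial test will be used".

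The decision itself is made on a one-sided 96% lower limit. For Cohort 3 the protocol says "The trial will be considered a success if the lower limit of 96% confidence interval is greater than 10" percent. For Cohort 2 the SAP (2.3.1) repeats the protocol's rule: "The trial will be considered a success if the lower limit of 96% confidence interval is greater than 5" percent.

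The only responder counts for these cohorts are in SAP 2.3.1, and they belong to the earlier, smaller two-stage designs: "if 5 or more patients out of 56 enrolled achieve CR or PR" for Cohort 2 and "if 6 or more patients out of 34 enrolled achieve CR or PR" for Cohort 3. Neither document gives a count for 70 or 52 patients. Cohorts 1 and 4, by contrast, have explicit final counts (13 of 46 and 8 of 84).

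Interval methods are mentioned only for other quantities. Protocol 12.4.7 uses an exact interval for "patients who experienced DLT with a 2-sided 95% exact binomial CI". SAP 3.8 says of clinical benefit rate that "Approximate 2-sided 95% CIs will be calculated for each cohort", and it applies a multistage adjustment to the two-sided 95% interval for response rate.

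**The concern.** With a binomial count, type I error and power move in steps, so a sample size from a continuous approximation may not deliver its nominal operating characteristics. If no integer cut-off meets both stated figures, at least one of them is wrong, and which one depends on the interval method that the plan leaves open.

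This limit decides success on the primary endpoint in two cohorts, and Protocol 12.1.2 ties the data in these cohorts to late-phase planning. The study is open-label, so a method left unspecified could be settled after the responses are known.

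**Working it through.** **Inputs** (Protocol 12.1.2). Cohort 2: n = 70, null rate p0 = 0.05, alternative p1 = 0.15. Cohort 3: n = 52, p0 = 0.10, p1 = 0.25. One-sided 5% overall, 4% at the final analysis, power 90%.

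**1. Reproducing the sample sizes.** The one-sample normal approximation is

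n = [(z(1−α)·√(p0(1−p0)) + z(0.90)·√(p1(1−p1))) / (p1 − p0)]²

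With one-sided α = 0.04, z = 1.751 and z(0.90) = 1.282:

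- Cohort 2: n = 70.4; nominal power at 70 is 89.9%.
- Cohort 3: n = 51.9; nominal power at 52 is 90.1%.

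At α = 0.05 the same formula rounds up to 67 and 49. The planned sizes therefore come from this approximation at 4%.

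**2. Binomial probabilities at those sizes.** Type I error is P(X ≥ r | n, p0); power is P(X ≥ r | n, p1).

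| Rule | Type I error | Power |
|---|---|---|
| at least 7/70 | 6.0% | 91.6% |
| at least 8/70 | 2.3% | 84.3% |
| at least 9/52 | 7.1% | 93.0% |
| at least 10/52 | 3.2% | 87.1% |

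Both quantities fall as r rises, so the adjacent cut-offs settle the matter: the lower one breaks 5% and the higher one misses 90%.

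**3. Is the alpha split the cause?** No. The exact lower limits at one-sided 95% are 0.0479 for 7/70, 0.0582 for 8/70, 0.0934 for 9/52 and 0.1082 for 10/52. These give the same cut-offs as at 96%. Suppose the administrative look counted as a chance of success at exact 1% (at least 7/42 and at least 8/31, which is an assumption). Power would then rise only to 84.5% and 87.4%.

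**4. The success rule under different methods.** One-sided 96% lower limits:

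| Result | Threshold | Exact (Clopper-Pearson) | Score (Wilson) | Wald |
|---|---|---|---|---|
| 7/70 | 0.05 | 0.0455 fail | 0.0531 succeed | 0.0372 fail |
| 8/70 | 0.05 | 0.0556 succeed | 0.0633 succeed | 0.0477 fail |
| 9/52 | 0.10 | 0.0896 fail | 0.1002 succeed | 0.0812 fail |
| 10/52 | 0.10 | 0.1041 succeed | 0.1149 succeed | 0.0966 fail |

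Wald first succeeds at 9/70 (type I error 0.8%, power 74.1%) and 11/52 (1.3%, 78.5%). Three common methods thus give three different cut-offs in each cohort.

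**5. Chance of landing on the count where score and exact disagree.** P(X = 7 | 70) is 3.7% at a true rate of 5% and 7.3% at 15%. P(X = 9 | 52) is 4.0% at 10% and 6.0% at 25%.

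**6. For reference only.** The smallest n with exact type I error within the level and power of at least 90%:

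- Cohort 2: n = 77 with at least 8 responders (3.8%, 90.7%), at either level.
- Cohort 3: n = 55 with at least 10 (4.4%, 91.1%) at 5%, or n = 59 with at least 11 (3.1%, 90.3%) at 4%.

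**The case against.** The strongest reply is that nothing was miscalculated. The sizes follow from a standard formula at one-sided 4%, and naming a binomial test most naturally implies an exact test with a matching limit. Type I error is then protected at 2.3% and 3.2%. Only power falls short, by 5.7 and 2.9 points, in single-arm cohorts meant to give preliminary evidence. On that view this is a clarification.

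The exact reading is the better-supported one, although neither document states it. It does not rescue the plan: if the limit is exact, the stated 90% power is wrong; if a score limit is used to keep 90%, the stated 5% is wrong. One figure must change on either reading.

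Three further points have some force:

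- The interval wording elsewhere concerns other quantities, so it shows silence on the 96% limit more than contradiction.
- The score success at 9/52 is marginal (0.1002 against 0.10), and the disagreement chances in step 5 apply only to the score and exact pair.
- The sizes of 70 and 52 are maxima, and the Full Analysis Set may be smaller. With an exact 96% limit the cut-off is 7 at n = 63 and 9 at n = 46, so fixed counts alone would not fit a reduced denominator. This shapes the remedy, but it does not remove the problem.

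**Conclusion.** The concern holds. At 70 and 52 patients the stated pair of one-sided 5% and 90% power cannot be achieved with any responder cut-off. An exact 96% limit gives 2.3%/84.3% (Cohort 2) and 3.2%/87.1% (Cohort 3). A score limit gives 6.0%/91.6% and 7.1%/93.0%, above both the 4% and the 5% level. As written, the primary success rule has no unique answer at 7/70 or 9/52. It applies to 70 + 52 = 122 of the 252 planned expansion patients, so it needs correcting before the analysis.

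These figures assume full enrolment, all patients in the Full Analysis Set, and a single-stage sample. SAP 2.3.1 says the design changed after these cohorts had entered their second stage. Suppose the earlier Stage 1 requirement (at least 2/20 and at least 2/13) is counted, with one response definition throughout. The exact rule then gives 1.8%/73.7% and 2.6%/78.9% jointly with passing Stage 1. Given that Stage 1 was passed, it gives 6.7%/89.4% and 6.8%/90.4%. The statement that the exact rule holds the level is therefore true unconditionally or jointly, but not conditionally on passing.

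**What to change.** In Protocol 12.1.2 and SAP 2.3.1 and 3.8:

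- Name the exact (Clopper-Pearson) one-sided 96% lower limit, equivalently the lower end of the two-sided 92% interval, as the decision interval, computed on the Full Analysis Set.
- State the resulting cut-offs at full enrolment: at least 8/70 and at least 10/52. The limit itself then governs if fewer patients are analysed.
- Replace the stated 5%/90% with 2.3%/84.3% for Cohort 2 and 3.2%/87.1% for Cohort 3.
- If another method is kept, state its count and its true type I error (for the score limit, 6.0% and 7.1%).
- If the Stage 1 requirement is reported, give type I error and power on one stated basis, joint or conditional.

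As a separate tidy-up, align the two-sided 98% interval for these cohorts in Protocol 12.4.5 with the 92% interval in SAP 3.8. The 98% interval is for reporting and is not the success rule, but only 92% matches a one-sided 96% limit.

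The cost is protocol and SAP wording and a less favourable stated power. No extra patients are needed.
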